4.2.1. Reproductive Restrictions

4.2.1.1. Women of Non-childbearing Potential

Women of non-childbearing potential are defined as female subjects who are permanently surgically sterilised or postmenopausal.

Permanent sterilisation includes hysterectomy and/or bilateral oophorectomy and/or bilateral salpingectomy at least 6 weeks before screening but excludes bilateral tubal ligation. Bilateral oophorectomy alone is acceptable only when the reproductive status of the woman has been confirmed by follow-up hormone level assessment.

Females are considered postmenopausal if they have had amenorrhea for at least 12 months or more following cessation of all exogenous hormonal treatments and without an alternative medical cause and the FSH level is in the postmenopausal range.

4.2.1.2. Male Subjects

Restrictions for Male Subjects

There is limited or no information about effects that SZC, cyclosporin, or tacrolimus could have on the development of the foetus in humans. Therefore, it is important that woman of childbearing potential, who are the partners of male subjects, do not become pregnant during the study and for a total period of 3 months after the male subject has attended the study follow-up visit.

Male subjects who have been sterilised are required to use one barrier method of contraception (condom) from the time of IMP administration until after the follow-up visit. The subject must have received medical assessment of the surgical success.

As a precaution, all non-sterilised male subjects should avoid fathering a child by either true abstinence¹ or use a condom and their female partner/spouse has to be either of non-childbearing potential or has to use a highly effective contraception form of birth control, starting from the time of IMP administration until 3 months after the study follow-up visit. The female partner/spouse should be stable on their chosen method of birth control for at least 3 months after the first IMP dosing.

Highly effective contraception form of birth control, ie, a form of birth control with a failure rate of less than 1% per year when used consistently and correctly, are:

- Combined (oestrogen and progestogen containing) hormonal contraception associated with inhibition of ovulation:
 - Oral
 - Intravaginal
 - Transdermal
- Progestogen-only hormonal contraception associated with inhibition of ovulation:
 - Oral
 - Injectable
 - Implantable
- Intrauterine device
- Intrauterine system
- Bilateral tubal occlusion of female partner

Sperm Donation

Male subjects should not donate sperm for the duration of the study and for at least 3 months after the study follow-up visit.

Pregnancy

Subjects will be instructed that if their partner becomes pregnant during the study, this should be reported to the Investigator. The Investigator should also be notified of pregnancy occurring during the study but confirmed after completion of the study. In the event that a subject's partner is subsequently found to be pregnant after the volunteer is included in the

¹ Sexual abstinence is defined as refraining from heterosexual intercourse during the entire period of risk associated with the study treatments. It is only acceptable if preferred and usual lifestyle of the subject.

study, then consent will be sought from the partner and if granted, any pregnancy will be followed and the status of mother and/or child will be reported to the Sponsor after delivery.

A pregnancy notification form and follow-up will be completed.

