6.3.1.2. Definitions of Serious Adverse Event

An SAE is an AE occurring during any study phase (ie, screening, treatment, washout, follow-up), that fulfils one or more of the following criteria:

- Results in death
- Is immediately life-threatening
- Requires in-patient hospitalisation or prolongation of existing hospitalisation
- Results in persistent or significant disability or incapacity or substantial disruption of the ability to conduct normal life functions
- Is a congenital abnormality or birth defect
- Is an important medical event that may jeopardise the subject or may require medical intervention to prevent one of the outcomes listed above

For further guidance on the definition of an SAE, see [Appendix A](#) of this CSP.

Adverse events for malignant tumours reported during a study should generally be assessed as SAEs. If no other seriousness criteria apply, the ‘Important Medical Event’ criterion should be used. In certain situations, however, medical judgment on an individual event basis should be applied to clarify that the malignant tumour event should be assessed and reported as a non-serious AE. For example, if the tumour is included as medical history and progression occurs during the study, but the progression does not change treatment and/or prognosis of the malignant tumour, the AE may not fulfil the attributes for being assessed as serious, although reporting of the progression of the malignant tumour as an AE is valid and should occur. Also, some types of malignant tumours, which do not spread remotely after a routine treatment that does not require hospitalisation, may be assessed as Non-Serious; examples include Stage 1 basal cell carcinoma and Stage 1A1 cervical cancer removed via cone biopsy.

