12.2. Pregnancy

All pregnancies and outcomes of pregnancy should be reported to AstraZeneca except:

- If the pregnancy is discovered before the study patient has received any IMP.

If a pregnancy is reported, the Investigator should inform the Sponsor within 24 hours of learning of the pregnancy.

Abnormal pregnancy outcomes (eg, spontaneous abortion, fetal death, stillbirth, congenital anomalies, ectopic pregnancy) are considered SAEs.

Please refer to Section 4.2.1.2 for further details.

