12.2.1. Paternal Exposure

Male subjects should refrain from fathering a child during the study and for 3 months following the last dose.

In case of pregnancy of the partner of a male patient, the partner's pregnancy should be reported on the pregnancy form (consent from the partner must be obtained before the pregnancy form is completed) following the same timeframe and routing as described for any subject's pregnancy. Pregnancy of the patient's partner is not considered to be an AE. These pregnancies will also be followed up, and the outcome of the pregnancy (spontaneous miscarriage, elective termination, ectopic pregnancy, normal birth or congenital abnormality) should, if possible, be obtained and documented.

Please refer to Section [4.2.1.2](#) for further details.

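### Subjects are told to report only partner pregnancies that begin during the study, although the stated risk period runs about 3 months longer and the protocol's pregnancy-reporting rules have no end date

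*Protocol*

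**What the plan says.** The instruction to subjects is in Section 4.2.1.2 under Pregnancy: "Subjects will be instructed that if their partner becomes pregnant during the study, this should be reported to the Investigator". The sentence after it reads: "The Investigator should also be notified of pregnancy occurring during the study but confirmed after completion of the study". It allows for late confirmation, but the pregnancy must still have begun on study.

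The period of concern in the same section is longer. Because information on foetal effects of the three products is limited or absent, partners of childbearing potential should "do not become pregnant during the study and for a total period of 3 months after the male subject has attended the study follow-up visit". Non-sterilised men follow the contraception rules "starting from the time of IMP administration until 3 months after the study follow-up visit". Section 12.2.1 uses a different end-point: "Male subjects should refrain from fathering a child during the study and for 3 months following the last dose".

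The rules on reporting and follow-up have no closing date:

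- Section 4.2.1.2 continues: "In the event that a subject's partner is subsequently found to be pregnant after the volunteer is included in the" study, the partner's consent is sought and, if it is given, the pregnancy is followed and the status of mother and/or child goes to the sponsor after delivery.
- Section 12.2 says: "All pregnancies and outcomes of pregnancy should be reported to AstraZeneca except" where the pregnancy is discovered before any IMP has been received.
- Section 12.2.1 requires a partner's pregnancy to be recorded on the pregnancy form, with the same timing and routing as a subject's pregnancy.

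The schedule of assessments (Table 3) ends with the follow-up visit, 7 to 10 days after the last dose.

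**The concern.** The rules in Sections 12.2 and 12.2.1 bind the investigator and the sponsor, who can act only on pregnancies they hear about. Female subjects must be of non-childbearing potential (Sections 4.1.1 and 4.2.1.1), so the pregnancies to be expected are in partners, who are not study participants. Once the follow-up visit is over, the site will normally learn of one only if the subject reports it.

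A subject who follows Section 4.2.1.2 to the letter has no reason to report a pregnancy that begins after the study, even within the 3 months that the section treats as a period of concern. The protocol would then miss cases that its other sections want reported and followed, on a question where it says information is scarce. The wording on late confirmation shows that reports after study completion were considered, but only for pregnancies that began on study.

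**Working it through.** The protocol gives no figure of its own to reproduce. The check is a day count of how much of the stated window falls outside the subject's instruction.

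**Inputs**

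- Gap between doses, *g*: at least 14 days, counted from the day after dosing (Table 4), so 14 or 15 days at minimum washout.
- Last dose to follow-up visit, *f*: 7 to 10 days (Section 3.1).
- Post-study period: 3 months after the follow-up visit (Section 4.2.1.2) or 3 months after the last dose (Section 12.2.1). I take 3 months as 91 days; this is an assumption.
- Total duration per subject: about 58 days including screening (Section 3.1.3).
- End of study: the last subject's last visit (Section 3.1.2).

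**Step 1. First dose to the subject's own follow-up visit**, *g* + *f*: from 14 + 7 = 21 days to 15 + 10 = 25 days.

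**Step 2. Period ends 3 months after follow-up (Section 4.2.1.2).** Share outside the instruction = 91 / (*g* + *f* + 91).

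- Highest: 91 / (21 + 91) = 91/112 = 81%.
- Lowest: 91 / (25 + 91) = 91/116 = 78%.

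**Step 3. Period ends 3 months after the last dose (Section 12.2.1).** Share = (91 − *f*) / (*g* + 91).

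- Highest: (91 − 7) / (14 + 91) = 84/105 = 80%.
- Lowest: (91 − 10) / (15 + 91) = 81/106 = 76%.

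Steps 2 and 3 together give 76% to 81%.

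**Step 4. How far this depends on where the study ends.**

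- Counting all 58 days as in-study: 91 / (58 + 91) = 91/149 = 61%.
- Taking the study to run to the last subject's last visit, the share falls for subjects enrolled early. As an illustration, assume the study closes 60 days after a subject's own follow-up visit: (91 − 60) / (21 + 91) = 31/112 = 28%.

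**Step 5. Break-even gap between doses.** With the study ending at the subject's own follow-up visit and the Section 4.2.1.2 end-point, half the window lies outside when *g* + *f* = 91, that is *g* = 81 to 84 days. The gap would have to be far above the 14-day minimum before the uncovered part stopped being the larger one.

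**The case against.** A reader might infer that the later months have no reporting instruction at all. The documents do not support that. The last sentence on pregnancy in Section 4.2.1.2, and Sections 12.2 and 12.2.1, all require reporting or follow-up without a time limit. What is missing is an instruction to the subject.

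A reader might also infer that abnormal outcomes are lost because the SAE definition in Section 6.3.1.2 stops at follow-up. That does not hold for partners. Section 6.3.1.1 defines an AE as something occurring in a subject, so a partner's outcome lies outside the SAE definition at any date. Section 12.2.1 deals with partners separately and asks for the outcome where it can be obtained. Section 4.2.1.2 already provides for a report after delivery, which for a pregnancy begun on study falls after the follow-up visit.

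Three further objections have weight:

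- **The share is fragile.** It depends on what counts as the study. Section 3.1.2 ends the study at the last subject's last visit, the cohorts are enrolled sequentially (Section 5.1.1), and the synopsis plans December 2020 to March 2021. Early enrolees could therefore be covered well past their own last visit. This stands, but it would make the duty depend on a date the subject does not know.
- **Days are not risk.** Dosing is two single-dose occasions, and Section 4.2.1.2 presents the contraception rule as a precaution. Suppose all 60 subjects were men with fertile partners using a method at the section's upper limit of 1% failure per year. Then 60 × 0.01 × 91/365 = about 0.15 pregnancies would be expected in the tail. This ignores condom use and assumes the method is used consistently and correctly. It stands as a limit on importance.
- **The subject information is not among the documents**, so what subjects are told in practice cannot be checked. The protocol wording is still narrower than its own rules.

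**Conclusion.** The point holds as a mismatch within the protocol. The subject is told to report partner pregnancies that begin on study, while the stated period of concern runs about 3 months longer and the reporting rules for the investigator and sponsor have no end date. With no contact scheduled after follow-up, those rules depend on the subject.

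About 76% to 81% of the window is outside the instruction, given the minimum washout, 91 days for 3 months, and a study that ends at the subject's own follow-up visit. Under the wider readings of the study's end the share is 61% or less. These are shares of calendar days and should not be read as shares of risk or of expected pregnancies.

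Two ambiguities add to the mismatch: the meaning of *during the study* for an individual subject, and the end-points in Sections 4.2.1.2 and 12.2.1, which lie 7 to 10 days apart. The point is minor. It concerns completeness of safety reporting and does not touch the PK results, the sample size or the analysis.

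**What to change.** In Section 4.2.1.2 (Pregnancy), in both the instruction sentence and the late-confirmation sentence, replace *during the study* with a window from first IMP administration to the end of the post-study period in which fathering a child is to be avoided. State that subjects are told, at or before the follow-up visit, how to report a partner pregnancy after their last visit.

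The sponsor should reconcile the end of that period between Section 4.2.1.2 (counted from the follow-up visit) and Section 12.2.1 (counted from the last dose), so that the new window points to one date. Section 4.2.1.2 also ends the barrier requirement for sterilised men after the follow-up visit, so the text should make clear which period sets the reporting window for them. Which end-point applies is for the sponsor to decide.

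Sections 6.3.1.2 and 12.2 need no change for this point. The cost is one or two sentences in the protocol and matching wording in the subject information. It adds no visits or tests, and at most a few extra pregnancy forms.

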4.3. Replacement of Subjects

As there is a goal of meeting a particular sample size in this study, the subjects who are withdrawn from the study due to AEs or changes in safety parameters will not be replaced unless required to meet the specific sample size for statistical purposes and if the Sponsor's responsible physician and the Investigator agree it is safe to do so. Subjects who withdraw or are withdrawn from the study for other reasons may be replaced following discussion with the Sponsor.

5. STUDY CONDUCT

5.1. Subject Enrolment and Randomisation

The Investigator will ensure:

- Signed informed consent is obtained from each potential subject before any study specific procedures are performed.
- Each potential subject is assigned a unique enrolment number at screening upon signing the informed consent.
- The eligibility of each subject is in accordance with the inclusion and exclusion criteria.
- Each eligible subject is assigned a unique randomisation code.

Randomisation can be done on the evening prior to the day of first IMP dosing.

Randomisation codes will be assigned strictly sequentially as subjects become eligible for enrolment (codes to be used without leading zero[s]).

When using unique enrolment number, the specific format must be followed (ie, reduced enrolment number “01001” in ClinBase™ and on labels, full enrolment number “E0001001” for outputs).

If a subject withdraws his/her participation in the study, then his/her randomisation code cannot be reused. If a replacement is mandated, replacement subjects will receive a new randomisation number and will be allocated to the same treatment sequence as the replaced subject.

5.1.1. Procedures for Randomisation

Upon completion of the randomisation requirements specifications form, the randomisation will be produced by Parexel according to the AstraZeneca randomisation system (AZRand).

Subjects will be enrolled into Cohort 1 and Cohort 2 sequentially.

Subjects in Cohort 1 and Cohort 2 will be randomised in a 1:1 ratio to receive one of the 2 treatment sequences and then cross-over to the other: Tacrolimus alone (treatment A) followed by the combination treatment of tacrolimus and SZC (treatment B) or vice versa in Cohort 1 and cyclosporin alone (treatment C) followed by the combination treatment of cyclosporin and SZC (treatment D) or vice versa in Cohort 2.

The randomisation will be completed for each cohort using consecutive randomisation codes.

The number of subject identifiers generated for the study will account for the number of enrolment subjects per the sample size calculation (N = 60 total, as N = 30 for each of the

2 cohorts and N = 15 for each of the 4 treatment sequence) as well as providing sufficient randomisation numbers for replacements. For this study, a total of 120 subject identifiers will be randomly assigned to the treatment sequence(s): AB|BA and CD|DC.

5.2. Procedures for Handling Incorrectly Enrolled Subjects

Subjects who fail to meet the inclusion criteria or meet any exclusion criterion should not, under any circumstances, be randomised into the study. There can be no exceptions to this rule. Where a subject, who does not meet the selection criteria, is randomised in error and this is identified before dosing, the subject should be withdrawn from the study. If a subject is withdrawn prior to dosing they will be replaced. If a subject, who does not meet the selection criteria and has been dosed before the error is identified, the subject should be withdrawn and advised to continue safety assessments to ensure their safety. The Investigator will inform the AstraZeneca Lead Physician of the error and a joint decision made as to whether the subject should be replaced.

5.3. Blinding

This is an open-label study and blinding is not applicable.

5.4. Treatments

5.4.1. Identity of the Investigational Medicinal Product

Details on the identity of the IMP are presented in [Table 5](#).

Table 5 Identity of the Investigational Medicinal Product

Investigational Medicinal Product Name	Sodium Zirconium Cyclosilicate	Tacrolimus	Cyclosporin
Trade Name:	Lokelma™	Prograf	Sandimmun Neoral/Optoral
Manufacturer:	AstraZeneca	Astellas Pharma	Novartis
Formulation:	Powder for oral suspension	Hard capsules	Soft capsules
Strength/concentration:	CCI Sachet	CCI	CCI
Dose:	CCI		
Route of administration:	Oral	Oral	Oral
Specific device for drug administration, if applicable:	Not applicable	Not applicable	Not applicable
Regimen:	Single dose of CCI consisting of 3 sachets suspended in 45 mL of water	Single dose of CCI	Single dose of CCI
Special handling requirements:	Not applicable	Not applicable	Not applicable

Details of the batch numbers will be included in the trial master file and the final CSR.

5.4.2. Supply of Investigational Medicinal Product

The IMP, SZC will be supplied by AstraZeneca in sachets packed in cartons.

The IMPs, tacrolimus and cyclosporin will be sourced by Parexel.

A technical agreement between the Investigator and AstraZeneca will be in place to cover all pharmacy related activities, detailing roles and responsibilities prior to receipt of the IMPs at the Clinical Unit.

A release document signed by a legally authorised Qualified Person will be placed in the appropriate section of the Trial Master File to document labelling and dispensing of the IMPs to the subject.

5.4.3. Dose and Treatment Regimens

Each subject will receive single oral doses of SZC and/or tacrolimus/cyclosporin under fasted conditions. The doses will be administered after an overnight fast of at least 12 hours.

Sodium zirconium cyclosilicate will be administered orally as suspension, containing **CCI** of IMP dissolved in 45 mL of water. Tacrolimus and cyclosporin will be administered as oral capsules for swallowing with 200 mL of non-carbonated water at room temperature.

On days of IMP co-administration, SZC will be administered immediately followed by tacrolimus/cyclosporin.

Subjects will be allowed to drink water to prevent dehydration until 1 hour before dosing. Water will be allowed ad libitum from 2 hours after dosing and a standard meal will be given 4 hours after dosing.

After dosing, subjects will remain semi-supine on their bed or sitting (except when necessary for study procedures) until 4 hours after dosing.

Other restrictions, including posture control are described in Section 4.2. Data of subjects may be excluded from the PK analysis set as described in Section 11.1.2.

5.4.4. Labelling

Labels will be prepared in accordance with GMP and local regulatory guidelines.

The labels will fulfil GMP Annex 13 requirements for labelling.

5.4.5. Storage and Handling Procedures

All IMPs will be stored in a secure facility, details of storage conditions will be provided on the label of the IMPs.

The AstraZeneca staff will be permitted upon request to audit the supplies, storage, dispensing procedures, and records.

5.5. Concomitant and Post-study Treatment(s)

Apart from paracetamol/acetaminophen, no concomitant medication or therapy will be allowed.

The subjects should be instructed that no other medication is allowed, including herbal remedies, vitamin supplements and OTC products, without the consent of the Investigator.

Medication, which is considered necessary for the subject's safety and well-being, may be given at the discretion of the Investigator during the in-house period. Such instances will be registered as important protocol deviations unless the medication is paracetamol/acetaminophen.

When any medication is required, it should be prescribed by the Investigator. Following consultation with AstraZeneca Lead Physician, the Investigator should determine whether or not the subject should continue in the study. Administration of concomitant medications may be documented as a protocol deviation after consultation of the Investigator with AstraZeneca Lead Physician.

5.6. Treatment Compliance

Dosing will take place at the Parexel Early Phase Clinical Unit.

The administration of all IMPs will be recorded in ClinBase™.

Compliance will be assured by direct supervision. After IMP administration, a check of the subject's mouth and hands will be performed.

5.6.1. Drug Accountability, Dispensing and Destruction

The IMPs provided for this clinical study will be used only as directed in this CSP.

In accordance with GCP, the investigational site will account for all supplies of SZC, tacrolimus and cyclosporin. Details of receipt, storage, assembly/dispensing and return will be recorded.

All unused supplies of all IMPs will either be destroyed by Parexel or returned at the end of the study in accordance with instruction by the Sponsor.

